**TABLE 1: TIME AND EVENTS SCHEDULE**

	Screening and Treatment Phase							Follow-Up Phase				
	DAY 0 (Clinic)	DAY 1 (Clinic)	DAY 2 (Phone) 	DAY 3* (Clinic)	DAY 4 (Phone)	DAY 5 (Phone)	DAY 6 (Clinic)	DAY 7 (Phone)	Day 17± 3	Unscheduled Clinic Visit 	Unscheduled Phone Visit 	DAY 30 ± 5 (Clinic)
Informed Consent	X											
Confirmation of Eligibility	X											
Randomization	X											
Medical History & Demographics	X											
Limited Physical Exam  including NYHA Class	X	X	X				X		X			X
Composite Congestion Score	X	X	X	X	X	X	X	X	X	X		X
5-Point Current Dyspnea Score	X	X	X	X	X	X	X	X	X	X		X
7-Point Dyspnea Score	X	X	X	X	X	X	X	X	X	X		X
Vital Signs (RR, BP, HR), Weight + Height (Day 0 only) 	X	X	X	X	X	X	X	X	X	X		X
Clinical Laboratory 	X	X	X				X		X			X
Urine Pregnancy Test 	X		X				X		X			X
NT-proBNP 	X						X		X			X
KCCQ-12	X						X		X			X
Patient Global Assessment VAS	X	X	X	X	X	X	X	X	X			X
Device/Product Training	X											
6MWT	X	X					X					X
ReDS Measurement 	X	X					X					X
Device/Product Administration 	X	X	X	X	X	X	X					
Device/Product Accountability	X	X					X		X			X
Subject Diary 	X	X	X	X	X	X	X	X	X	X		X
Adverse Events	X	X	X	X	X	X	X	X	X	X		X
Concomitant Medications	X	X	X	X	X	X	X	X	X	X		X
Schedule Next Study Visit	X	X	X				X	X	X	(If Necessary)	(If Necessary)	

\* If Day 3 falls on a Saturday or Sunday, subjects may be seen in the clinic and have Day 3 assessments completed on either Day 2 (Friday if Day 3 falls on Saturday) or Day 4 (Monday if Day 3 falls on Sunday). On Day 3 the subject will have a phone call visit.

Limited PE includes minimally evaluation of the skin of abdominal area, lungs/chest, heart, abdomen and periphery.

Vital signs include respiratory rate (RR), blood pressure (BP) and heart rate (HR) and will be obtained at clinic visits. BP and HR will be obtained with phone assessments. Weight, BP and HR should be obtained at home each day in the morning after Day 0, even on clinic visit days. Height recorded Day 0 only.

Clinical Labs are done locally and include BUN, Cr, Na+, K+, Cl, CO2, and Mg; Day 0 NT-proBNP will be done locally to determine eligibility and 2nd sample sent to centralized lab for subjects who qualify. NT-proBNP drawn Day 3, Day 7 and Day 30 will be done at centralized lab.

Urine pregnancy test on females of childbearing potential.

Scheduled Phone Calls will have a written script to guide the site staff on what questions to ask the Subject.

Remote Dielectric Sensing (ReDS) System for % lung fluid measurement.

If modifications are made to the diuretic regimen after Subjects are transitioned to their oral maintenance diuretic regimen, including additional doses of Furoscix for the treatment group or oral diuretics for the treatment as usual control group, the Subject will have follow-up assessments and timing of those assessments based on the investigator's clinical judgement and document those under Unscheduled Visit (clinic or phone) column. Unscheduled clinic and phone visits can be conducted as needed.

If Subject receives unscheduled at-home phone call, the staff should perform assessments in the Unscheduled Phone Visit column.

Device issues should be recorded by the subject in the comments/Issues section of the Subject Diary. For each device issue recorded by the subject, a Device Issue Intake Form should be completed and submitted to the sponsor by the study staff.

### **3. TREATMENT**

**Study Drug:** Furoscix, (Furosemide Injection), 80 mg/10 mL is a proprietary furosemide formulation that is buffered to a neutral pH to enable subcutaneous administration and contained in a prefilled Crystal Zenith® (CZ) cartridge.

**Study Device:** The Infusor is a compact, ethylene oxide (EtO) sterilized, single-use, electro-mechanical (battery powered, micro-processor controlled), on-body subcutaneous delivery system based on the SmartDose® Gen II 10 mL (West Pharmaceutical Services).

The Furoscix Infusor is an investigational drug-device combination product. The Infusor is applied to the abdomen via a medical grade adhesive and delivers a subcutaneous infusion of Furoscix through a pre-programmed, biphasic delivery profile with 30 mg (3.75 mL) administered over the first hour, followed by 12.5 mg (1.56 mL) per hour for the subsequent 4 hours (Total dose is 80 mg (10 mL) over 5 hours).

### **4. SAMPLE SIZE**

Fifty-one (51) subjects will be included and randomly assigned in a 2 to 1 ratio to receive Furoscix (n=34) or continued medical therapy (n=17) in the home setting with 30 days of follow-up. Given the exploratory nature of this study, no formal power analysis of sample size was conducted.

### **5. CENTERS**

This is a Multicenter, Randomized, Open Label, Controlled Study to be conducted at up to 20 sites.

### **6. OBJECTIVES**

#### **6.1 Primary Objective:**

Provide pilot data on effectiveness and safety to inform a pivotal trial

#### **6.2 Secondary Objectives:**

- Inform population enrichment strategies
- Refine pivotal trial endpoints and analytical methods
- Identify operational challenges of study design
- Assess patient adherence, competence, and experience
- Familiarize staff and patients with device application and use

### **7. DATA ANALYSIS CONSIDERATION**

#### **7.1 General Data Considerations:**

The following conventions will be applied to analyses/data presentation:

All dates will be displayed in DDMMYY format.

Repeat assessments will be considered as unscheduled. Unscheduled visit data will be presented in Listings, but not in Tables and Figures.

The statistical analyses will be performed using Statistical Analysis System (SAS) Version 9.3 (or higher). All Tables, Listings and Figures (TLFs) will be produced in landscape format. In general, all data collected during the study will be presented in the data listings. Unless otherwise noted, the data will be sorted first by treatment group, then by subject number, and then by date within each subject number. The number of variables presented in each listing can vary. Please refer to Mock tables, listings, and figures.

Data will be summarized by treatment group where appropriate. The total number of subjects (N) in the treatment group under the stated population will be displayed in the header of summary tables.

Data will be summarized using descriptive statistics for continuous variables. Unless otherwise stated, descriptive statistics will include number of subjects (n), mean, standard deviation (SD), minimum, median, and maximum. When n=0, except n, all other summary statistics will be kept blank. In case n=1, only n, minimum and maximum will be reported, and all other summary statistics will be kept blank. The statistic “Missing” will also be evaluated by enumerating the number of missing entries/subjects, if any at that visit, and presented as a summary statistic only for the resulting visits.

For categorical variables, data will be summarized using counts and percentages. The number [n] indicates the actual number of subjects with a particular value of a variable or event, which should always be less than or equal to the total number of subjects in the respective treatment group [N]. The number and percentage of subjects with missing values for a variable/category/event will also be presented for the resulting visits under the “Missing” category. Percentage will be obtained by:  $\% = (n/m) * 100$ , where m is the number of subjects present at that visit. Unless otherwise stated, all percentages will be expressed to one decimal place. The number and percentage of subjects will always be presented in the form XX (XX.X). Counts of zero in any category will be presented as “0” and if the percentage in any category to be presented is 100, it will be presented as “100”.

The laboratory assessment values that are LLOQ (lower limit of quantification) will be converted to numeric values such as “<1” = 1 or “<5” = 5.

Tables that involve statistical modeling will not be presented if the model fails due to excessive missing data (e.g., GEE model fails to converge).

When analyzing statistical models (e.g. GEE models), if the unstructured covariance structure fails to converge then different covariance structures (e.g., Exchangeable (EXCH/CS), Independence (IND), Autoregressive(1)) will be applied.

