6.1.3. Assessment of Adverse Events of Special Interest

Subjects will have blood drawn at each clinic visit to monitor safety parameters. Subjects will specifically be monitored for the following adverse events:

- Worsening kidney function, defined as increase of ≥ 0.5 mg/dl in serum creatinine
- Hyperkalemia, defined as $K > 5.5$ mEq/L
- Hypokalemia, defined as $K < 3.5$ mEq/L
- Hypomagnesemia, defined as $Mg < 1.5$ mg/dL

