6.2. Study Phases and Procedures

A Time and Events Schedule is provided in [Appendix 1](#).

The Screening Phase will be conducted in the clinic. All Subjects who sign the informed consent form and satisfy the inclusion/exclusion criteria will be enrolled into the trial on the same day as screening. NT-proBNP will be sent to centralized laboratory. Drug administration will start on the day of screening and enrollment after randomization.

The Treatment Phase will begin upon completion of screening through Day 29. Furoscix will be administered via the Furoscix Infusor whereby 80 mg is administered subcutaneously over 5 hours in a biphasic regimen (30 mg in the first hour, followed 12.5 mg/hour for the subsequent 4 hours). Within a single 24-hour period, the 80 mg dose can be repeated at the discretion of the investigator ≥ 2 hours after the completion of the first dose. Subjects should be transitioned back to their oral maintenance diuretic regimen when clinically indicated at the discretion of the investigator. After Subjects have been transitioned to their oral maintenance diuretic regimen, additional doses of Furoscix can be prescribed during the 30-day study period as needed based on the presence of congestion symptoms (dyspnea, edema, and/or excess weight gain) as determined by the investigator. No more than 7 doses of Furoscix is permitted during the 30-day study period. Additional doses beyond 7 requires approval by the medical monitor.

Prior to leaving the clinic on Day 0, the Subject and/or caregiver will be trained by the study staff on how to prepare the study product and apply it to their abdomen and remove it once the infusion is completed. The initial dose of the study product may be administered in the clinic or at home on the day of enrollment. Additional doses will be provided to the Subject for self-administration or administration by a caregiver in the home setting as directed by the investigator or study staff.

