6.2.10. Unscheduled Visit (In-Clinic Visit)

If subjects experience worsening signs and symptoms they can be seen in the clinic as an unscheduled visit. For subjects presenting for an unscheduled visit the following assessments may be performed:

- Limited physical exam including NYHA Classification
- CCS (Composite Congestion Score)
- 5-point Current Dyspnea Score (using the script - [Appendix 7](#))
- 7-point Dyspnea Score (using the script – [Appendix 7](#))
- Weight
- Vital Signs
- % Lung Fluid Measurement (ReDS)
- Labs drawn for safety analyses (local laboratory) and NT-proBNP (send to centralized laboratory)

- Review Subject Diary for completeness and any recorded device issues
- Review any changes to concomitant medications since last visit
- Assess for adverse events
- Evaluate the clinical response to diuretic therapy and adjust as needed. For Furoscix subjects, additional doses may be prescribed. More than 7 doses of Furoscix in the 30-day study period require approval by the medical monitor. For subjects receiving continued medical therapy with oral diuretics, investigators will determine whether any modifications are needed. If diuretic modifications are made after Subjects' are transitioned to their oral maintenance diuretic regimen, including additional doses of Furoscix in the treatment group or oral diuretics for the treatment as usual control group, the Subjects' follow-up assessments and timing of those assessments will be based on the investigator's clinical judgement. Additional unscheduled clinic and phone visits can be conducted as needed.

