¹Limited PE includes minimally evaluation of the skin of abdominal area, lungs/chest, heart, abdomen and periphery.

²Vital signs include respiratory rate (RR), blood pressure (BP) and heart rate (HR) and will be obtained at clinic visits. BP and HR will be obtained with phone assessments. Weight, BP and HR should be obtained at home each day in the morning after Day 0, even on clinic visit days. Height recorded Day 0 only.

³Clinical Labs are done locally and include BUN, Cr, Na⁺, K⁺, Cl, CO₂, and Mg; Day 0 NT-proBNP will be done locally to determine eligibility and 2nd sample sent to centralized lab for subjects who qualify. NT-proBNP drawn Day 3, Day 7 and Day 30 will be done at centralized lab.

⁴Urine pregnancy test on females of childbearing potential.

⁵Scheduled Phone Calls will have a written script to guide the site staff on what questions to ask the Subject.

⁶Remote Dielectric Sensing (ReDS) System for % lung fluid measurement.

⁷If modifications are made to the diuretic regimen after Subjects' are transitioned to their oral maintenance diuretic regimen, including additional doses of Furoscix for the treatment group or oral diuretics for the treatment as usual control group, the Subject will have follow-up assessments and timing of those assessments based on the investigator's clinical judgement and document those under Unscheduled Visit (clinic or phone) column. Unscheduled clinic and phone visits can be conducted as needed.

[figure not shown]
⁸If Subject receives unscheduled at-home phone call, the staff should perform assessments in the Unscheduled Phone Visit column.

⁹Device issues should be recorded by the subject in the comments/issues section of the Subject Diary. For each device issue recorded by the subject, a Device Issue Intake Form should be completed and submitted to the sponsor by the study staff.

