## 2. STUDY DESIGN

This is a multicenter, randomized, open label, controlled study evaluating the effectiveness, and safety of the Furoscix Infusor versus continued medical therapy in patients with chronic heart failure and fluid overload requiring augmentation in diuretic therapy outside of an acute care setting. 51 subjects will be randomly assigned (2:1) to receive Furoscix (n=34) versus continued medical therapy (n=17). Within a single 24-hour period, the 80 mg dose can be repeated at the discretion of the investigator  $\geq 2$  hours after the completion of the first dose. Subjects should be transitioned back to their oral maintenance diuretic regimen when clinically indicated at the discretion of the investigator. After Subjects have been transitioned to their oral maintenance

diuretic regimen, additional doses of Furoscix can be prescribed during the 30-day study period as needed based on the presence of congestion symptoms (e.g., dyspnea, edema, and/or excess weight gain) as determined by the investigator. No more than 7 doses of Furoscix are permitted during the 30-day study period. Additional doses beyond 7 requires approval by the medical monitor. Over the initial 7 days, all subjects will receive daily clinic or phone follow-up by the study staff. Decision of treatment with Furoscix in the intervention arm (Furoscix On-Body Infusor) as well as changes in oral diuretic dosing in the continued medical therapy group will be determined by the treating physician in coordination with the study nurse. Safety labs will be done on Days 1, 3, 7 and 30.

Each Subject will complete Screening, Treatment, and Follow-Up Phases on an outpatient basis. During the Screening Phase, all Subjects who sign the informed consent form and satisfy the inclusion/exclusion criteria will be enrolled into the trial. Drug administration will start on the day of enrollment (same day as screening after all eligibility criteria have been confirmed) after randomization.

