#### **15.3.4 Laboratory Parameters**

Descriptive statistics will be presented for observed and change from baseline values of each laboratory parameter (BUN, Cr, Na+, K+, Cl, C02, and Mg) and cardiac biomarker (NT-proBNP). Individual subject data listings of laboratory results will be presented. The clinically significant (defined as greater than twice the upper reference value or less than  $\frac{1}{2}$  the lower reference value) laboratory results will also be flagged.

Additionally, Laboratory data will be summarized by displaying shifts from baseline result (Low/Normal/High) to post-baseline visits by treatment group.

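### Unscheduled laboratory results are barred from all tables, so the SAP 15.3.4 laboratory tables hold no scheduled value between Day 7 and the Day 30 visit, and the adverse-event route fills that gap only in part

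*SAP*

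**What the plan says.** SAP 7.1 sets two conventions: "Repeat assessments will be considered as unscheduled", and "Unscheduled visit data will be presented in Listings, but not in Tables and Figures". Neither SAP 7.1 nor SAP 15.3 makes an exception for safety data.

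On timing, SAP 2 says "Safety labs will be done on Days 1, 3, 7 and 30", and the schedule adds a Day 0 draw. The only scheduled contact between Day 7 and Day 30 is the Day 17 ± 3 telephone call (protocol 6.2.8), which has no blood draw. Treatment remains possible in that interval: "The Treatment Phase will begin upon completion of screening through Day 29" (protocol 6.2).

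If Furoscix is given again, or oral diuretics are changed, after transition to oral maintenance, footnote 7 of protocol Appendix 1 tells sites to "document those under Unscheduled Visit (clinic or phone) column" the resulting follow-up assessments. The SAP schedule repeats the footnote. Protocol Appendix 1 marks the clinical laboratory panel for the unscheduled clinic visit.

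For the tables, SAP 15.3.4 plans descriptive statistics for each analyte and says "Laboratory data will be summarized by displaying shifts from baseline result (Low/Normal/High) to post-baseline visits by treatment group". It defines no worst-value summary. SAP 15.3.1 to 15.3.3 separately tabulate subjects with adverse events, SAEs and AESIs. SAP 10.3 defines the four AESIs by creatinine, potassium and magnesium thresholds over 30 days.

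**The concern.** Renal and electrolyte disturbance is the harm that the plan singles out: all four AESIs are laboratory-defined. The primary objective includes safety data to inform a pivotal trial. Blood drawn because a subject worsened, or because treatment was changed late, is among the most informative safety data in the study. Under SAP 7.1 those results are listed by subject but enter no by-arm laboratory summary.

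Take a subject whose potassium falls after a Day 15 re-dose and is normal again by the Day 30 visit. If the scheduled values were all normal, the shift table shows that subject as normal throughout. Whether the episode is counted anywhere by arm then depends on whether it was reported as an adverse event or AESI.

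**Working it through.** The plan states no figure on this point, so the check follows a late laboratory result from the visit to the table.

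**Data flow**

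1. Scheduled draws: Days 0, 1, 3, 7 and 30 ± 5. Draws scheduled strictly between Day 7 and the Day 30 visit: 0.
2. Late re-dosing needs an unscheduled visit. Protocol 6.2.8 requires an in-clinic evaluation before further Furoscix is prescribed at the Day 17 call, and no scheduled clinic visit exists at that time.
3. Follow-up of such a change goes to the unscheduled column (footnote 7), where a laboratory draw is marked.
4. SAP 7.1 sends that column, and any repeat, to listings only.
5. SAP 15.3.4 adds nothing that brings these results back.

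**Length of the gap**

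Gap = day of final visit − 7; share = gap ÷ day of final visit.

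| Final visit | Gap (days) | Share of follow-up |
|---|---|---|
| Day 25 | 25 − 7 = 18 | 18/25 = 72% |
| Day 30 | 30 − 7 = 23 | 23/30 = 77% |
| Day 35 | 35 − 7 = 28 | 28/35 = 80% |

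**What the final draw could catch (illustration only)**

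Assume that the last draw is exactly on Day 30, that onset is equally likely on each of Days 8 to 29 (22 days), and that an abnormality lasts L days. The documents give no durations. An episode starting on day s is still present on Day 30 if s + L − 1 ≥ 30.

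- L = 1: no onset day qualifies, 0/22 = 0%.
- L = 3: s = 28 or 29, 2/22 = 9%.
- L = 7: s = 24 to 29, 6/22 = 27%.

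**Other routes into a safety table**

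- *Adverse-event and AESI tables.* These count subjects and are not tied to visits, so a late abnormality can enter. Protocol 7.7.3 requires a clinically significant value to be recorded if it meets the adverse-event definition, and the investigator judges significance. Protocol 7.1 generally excludes laboratory abnormalities that have no symptoms and need no intervention, whereas protocol 6.1.3 lists the AESI thresholds themselves as adverse events. SAP 15.3.3 does not say whether AESIs come from reported events or from laboratory data or, if the latter, whether unscheduled values count.
- *Early withdrawal.* Protocol 4.3 asks, as far as possible, for the follow-up visit procedures. The SAP has no visit-window rule, so these values might be tabulated as the final visit.
- *Clinical-significance flag (SAP 15.3.4).* This needs a value above twice the upper or below half the lower reference limit. A potassium of 3.4 mEq/L meets the hypokalemia AESI (below 3.5) but would be flagged only if the lower limit exceeded 2 × 3.4 = 6.8 mEq/L. The flag is therefore no substitute for the AESI thresholds.

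**The case against.** The strongest reply is that the harms at issue already have their own tables. AESI incidence is part of a primary endpoint, covers 30 days and is independent of visit. In the potassium example, a value below 3.5 meets the AESI definition, and if it needed treatment it falls outside the general exclusion in protocol 7.1. This stands as far as it goes. A reader might infer that no late laboratory value can reach any safety table, and the documents do not support that. What remains open is the asymptomatic, untreated abnormality and the unstated source of the AESI counts.

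Other stronger readings also fail:

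- *The exclusion favours Furoscix.* Re-dosing exists only in that arm, but control-arm oral diuretic changes go to the same column, and subjects in either arm may attend unscheduled for worsening. The documents do not show which arm would lose more results.
- *All later follow-up is unscheduled.* Footnote 7 covers only changes made after transition to oral maintenance. The Day 17 call and Day 30 visit remain scheduled.
- *Vital signs have the same gap.* They do not: blood pressure, heart rate and weight are recorded at home daily and reviewed at the Day 17 call.

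It is also fair to say that leaving unscheduled values out of by-visit summaries is a common convention, that listings for 51 subjects can be read, and that the mock tables to which SAP 7.1 refers are not available here. The convention suits by-visit means. As written, though, the rule covers every table and figure, and a listing does not give a comparison by arm.

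**Conclusion.** The point holds for the laboratory tables. The SAP 15.3.4 descriptive and shift tables contain no scheduled value for 23 days (18 to 28 with the visit window), about three-quarters of follow-up, while re-dosing is possible through Day 29. Early-withdrawal assessments aside, results from that interval reach a safety table only through adverse-event or AESI reporting, which is incomplete as specified.

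The length of the gap follows directly from the schedule. How many results are affected is unknown, because the documents give no frequency of late re-dosing or of unscheduled draws. The 0%, 9% and 27% catch rates rest on assumed durations and uniform onset, and they only illustrate that one final draw is a weak detector of short episodes. No bias in favour of either arm is established. The data are collected and listed, so this is a correctable weakness in the summaries, worth fixing before the analysis.

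A secondary wording point concerns the draws themselves. Protocol 6.1.3 says "Subjects will have blood drawn at each clinic visit to monitor safety parameters", while 6.2.10 introduces a list that includes the safety laboratory draw with "For subjects presenting for an unscheduled visit the following assessments may be performed". The first may mean only the planned visits, since protocol 1.2.3 mentions creatinine and electrolytes after listing the four planned visits. The text leaves this unsettled.

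**What to change.** 1. **SAP 7.1.** Limit the exclusion of unscheduled and repeat data to by-visit summaries.
2. **SAP 15.3.4.** Add a by-arm shift table from baseline to the worst post-baseline value (lowest and highest potassium, lowest magnesium, highest creatinine), using all scheduled, repeat and unscheduled results.
3. **AESI thresholds.** Tabulate by arm the subjects whose laboratory values cross the SAP 10.3 thresholds, from the same full set of results. State in SAP 15.3.3 whether the AESI table uses reported events or laboratory data.
4. **Protocol 6.1.3 and 6.2.10.** Reconcile the two passages on blood draws at unscheduled clinic visits.

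The cost is one SAP sentence on scope, one on the AESI source, a few tables and a protocol wording change. The added tables need no new data collection. The drawback is unequal opportunity: a subject with more draws has more chances of an extreme value. The number of draws per arm should therefore stand beside the tables, also as draws per subject because the planned arms are 34 and 17.

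The safety population is defined by receipt of at least one dose of the investigational product. The sponsor should confirm that control subjects are included in these tables; otherwise they give no comparison by arm.
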